8.3 Sample size calculation

This study is an observational registration study - a descriptive study without comparison and formal hypothesis test, and the determination of sample size is not based on statistical considerations. The follow-up time and sample size are consistent with the overall objectives of the study. Considering the Guidelines for Clinical Trials of Aortic Stent-Graft System, the sample size is calculated to be 200 cases.

8.4 Criteria for termination of the study based on statistics

This study does not pre-establish interim analysis and the corresponding premature termination criteria, so this section is not applicable.

As a real-world study, the subjects will be followed up for 5 years. Periodic data statistical analysis is planned for 30 days, 6 months, 12 months, and 2-5 years post-procedure surgery. All statistical analyses shall be performed after the data have been collected, cleaned, and finally locked.

8.5 Procedures for processing missing, unused, incorrect or unreasonable data

Statistical analysis will be undertaken in accordance with the corresponding standard operating procedure (SOP). Refer to the relevant documentation for details. Incorrect data will be identified and rectified during the data cleaning process prior to statistical analysis. Data relating to patients who have withdrawn from the study will be included in the final statistical analysis. Specific reasons for all patients who have withdrawn from the study will be described in the statistical report. Missing data relating to the study's primary endpoint caused by premature withdrawal will be imputed in accordance with the above-mentioned strategy for missing values. This imputation process will not be performed for missing data relating to any other endpoints.

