3.2 Project contents

The study is designed as a prospective, multi-centre, post-market, real-world observational registry study. Continuous enrollment is to be conducted for all subjects treated with Minos™ Abdominal Aortic Stent-Graft and Delivery System who meet the inclusion criteria and who voluntarily consent to participate in the study. An enrollment duration period of 24 months is expected for this project and initially, 200 subjects (170 in China and at least 30 in Europe) are to be enrolled. Patient follow up – including CT imaging - will be undertaken in accordance with the usual standard of care at participating sites, and is expected to occur at 30 days, 6 months, 12 months and 2-5 years post-procedure.

1. Primary endpoint

- Technical success rate at 12 months

2. Secondary endpoints

- Incidence of major adverse events at 30 days
- Immediate technical success rate
- Incidence of successful aneurysm treatment at 2-5 years
- All-cause mortality up to 5 years post-procedure
- Aortic aneurysm related mortality up to 5 years post-procedure
- Secondary intervention rates up to 5 years post-procedure
- Aneurysm diameter and variation in aneurysm diameter from 30 days to 5 years post-procedure
- Incidence of type I, III endoleaks from 30 days to 5 years post-procedure
- The incidence rate of stent migration, fracture, stenosis, occlusion and distortion from 30 days to 5 years post-procedure

3. Other endpoints: technical success rate of Hercules balloon and incidence of balloon rupture, where applicable.

In this study, immediate technical success rate, technical success rate at 12 months, secondary intervention rate, aneurysm diameter and variation in aneurysm diameter, and the incidence of type I and III endoleaks are used as efficacy indicators of the Minos™ Abdominal Aortic Stent-Graft and Delivery System. The incidence of 30-day major adverse events, all-cause mortality, aneurysm related mortality, stent migration, stent fracture, stenosis, occlusion and distortion are used as safety indicators of the Minos™ Abdominal Aortic Stent-Graft and Delivery System.

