7.1.5 Primary endpoint

Successful aneurysm treatment: on the basis of technical success and during the follow-up period, the absence of aneurysm rupture, continuous type I and III endoleaks after operation, aneurysm enlargement (aneurysm diameter increased by more than 5mm), secondary intervention due to endoleak, stent occlusion or migration, including open surgery and endovascular surgery. Expected secondary interventions will not be included in the analysis.

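### Sections 8.2 and 8.5 put the 12-month and the 2-5-year treatment-success rates on different bases, and the late percentages can err in either direction

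*Protocol*

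**What the plan says.** Protocol section 7.1.5, headed as the primary endpoint, defines a cumulative composite: "Successful aneurysm treatment: on the basis of technical success and during the follow-up period, the absence of aneurysm rupture". It goes on to require freedom from continuing type I or III endoleak, from enlargement and from certain secondary interventions. Section 3.2 gives the primary endpoint another name, "Technical success rate at 12 months", and lists "Incidence of successful aneurysm treatment at 2-5 years" among the secondary endpoints.

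Section 8.5 makes three statements on missing data:
- On the 12-month primary outcome: "Missing data relating to the study's primary endpoint caused by premature withdrawal will be imputed in accordance with the above-mentioned strategy for missing values".
- On the records of those who leave early: "Data relating to patients who have withdrawn from the study will be included in the final statistical analysis".
- On every outcome apart from the primary one: "This imputation process will not be performed for missing data relating to any other endpoints".

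The strategy that the first statement points back to is not set out anywhere earlier in the protocol. Section 8.5 itself refers only to a standard operating procedure and related documentation.

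Section 8.2 gives categorical outcomes a frequency, a percentage and an exact binomial 95% interval. It assigns Kaplan-Meier analysis to all-cause and aneurysm-related mortality, secondary intervention and further safety measures. The success composite is not named there. The efficacy list in section 3.2 includes "immediate technical success rate, technical success rate at 12 months, secondary intervention rate, aneurysm diameter and variation in aneurysm diameter" and endoleak. The 2-5-year success rate appears in neither the efficacy list nor the safety list.

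**The concern.** If section 7.1.5 governs, one composite is reported at 12 months with withdrawals imputed, and at 2, 3, 4 and 5 years without. Readers will set these values side by side as a yearly series. A difference between year 1 and year 2 then mixes real failures with a change of method.

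The later values have a second weakness. A crude percentage takes no account of unequal follow-up, and section 8.2 does not say who is in the denominator. A patient who withdraws without failure at year 3 could be dropped at year 5, or counted as a success because no failure was seen. A patient who failed at year 2 and then left could be kept or dropped.

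This matters because section 4 gives medium- and long-term outcome as the reason for the registry. Incomplete follow-up is also foreseeable: section 7.2 keeps patients in the study when their follow-up is not completed.

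**Working it through.** **Inputs from the protocol.** The only success rate given is from the pre-approval study in section 4: 121/136 = 88.97%, which reproduces the stated 89%. The planned sample is 200 (section 8.3). The protocol gives no withdrawal rate and no late failure rate, so those below are assumptions.

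**Step 1: the late percentage under three denominators.** Assume 89% success at 12 months, with all patients seen then. Each year afterwards, 8% of those still followed are lost regardless of outcome, and then 4% of the remaining event-free patients fail.

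True 5-year success: 0.89 × 0.96⁴ = 0.756.

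Event-free and still followed, as a share of the cohort: S(k) = S(k−1) × 0.92 × 0.96. New observed failures: S(k−1) × 0.92 × 0.04.

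| Year | Event-free and followed | New observed failures | Known failures, cumulative |
|---|---|---|---|
| 1 | 0.890 | – | 0.110 |
| 2 | 0.786 | 0.033 | 0.143 |
| 3 | 0.694 | 0.029 | 0.172 |
| 4 | 0.613 | 0.026 | 0.197 |
| 5 | 0.542 | 0.023 | 0.220 |

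The 5-year percentage is then:
- Known failures kept, lost non-failures dropped: 0.542 / (0.542 + 0.220) = 71.1%, which is 4.5 points below the truth.
- Only patients still seen: 75.6%. This is correct here because loss is unrelated to outcome.
- No observed failure counted as success: 1 − 0.220 = 78.0%, which is 2.4 points above the truth.

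The same data thus span 78.0 − 71.1 = 6.9 points, through the denominator alone.

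**Step 2: the change of basis between 12 months and 2 years.** Assume 200 patients, 10% yearly withdrawal unrelated to outcome, and 3% failure in the second year. At 12 months 180 are seen, of whom 160 are successes. At 2 years 162 are seen, of whom 140 are successes. The unimputed 2-year rate among those seen is 140/162 = 86.4%. The 12-month rate depends on the unstated imputation rule:

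| 12-month rule | 12-month rate | Apparent change to 2 years |
|---|---|---|
| Missing = failure | 160/200 = 80.0% | +6.4 points |
| Missing at random | 160/180 = 88.9% | −2.5 points |
| Missing = success | 180/200 = 90.0% | −3.6 points |

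The underlying fall is from 88.97% to 88.97% × 0.97 = 86.3%, or about 2.7 points. The missing-at-random row differs from it only through rounding to whole patients. Across assumed withdrawal of 3-15% and failure of 2-5% a year, the apparent change with missing = failure runs from −1.8 to +11.6 points. It is a rise only when withdrawal exceeds new failure.

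**The case against.** The strongest reply is that section 8.5 is a legitimate choice. This is a descriptive registry without hypothesis tests (section 8.3), and imputing only the primary endpoint is common. Methods for secondary endpoints are often left to a statistical analysis plan, which is not shown here. Section 8.2 assigns effectiveness analysis to the full analysis and per-protocol sets, and treatment success is plainly effectiveness, so its absence from the section 3.2 lists looks like an omission. Much of this stands. It does not make the yearly series comparable, however, and an analysis plan that extended the imputation to years 2-5 would contradict section 8.5.

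Two stronger readings are tempting but unsupported.

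- A reader might infer that section 8.5 forbids any handling of missing data after 12 months. It excludes only the imputation used for the primary endpoint. Withdrawn patients' data stay in the analysis, and an analysis with censoring is unassigned, not forbidden. The 12-month imputation is itself limited to premature withdrawal, so a missing scan in a patient still in the study is imputed at neither time.
- A reader might infer that a failing device would show a flat curve because failed patients leave. With 2% yearly failure and yearly losses of 24% after failure and 8% otherwise, the rate among those seen does stay at 88.8-89.0% while the truth falls to 0.89 × 0.98⁴ = 82.1%. But this requires deleting recorded failures from a cumulative endpoint, which fits poorly with keeping withdrawn patients' data. If known failures are kept and lost non-failures dropped, the same scenario gives 0.588 / (0.588 + 0.166) = 77.9%, which is too low rather than flat.

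The label conflict also limits the point. If the primary endpoint really is technical success as section 3.2 names it, no 12-month composite is imputed and the change of basis disappears. The crude late percentages remain.

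**Conclusion.** The point holds in a limited form. Taking section 7.1.5 as the primary definition, the composite has withdrawals imputed at 12 months and not at 2-5 years. The only method that section 8.2 clearly gives the later rates is a crude percentage without a stated denominator. The rates are not on one basis. Under the assumptions in step 1, the 5-year figure lies between 4.5 points too low and 2.4 points too high.

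The direction of error cannot be read from the protocol. It depends on the unstated 12-month strategy, on the denominator, and on whether loss is related to outcome. All loss and late-failure rates above are assumed; only the 89% is the protocol's own. The finding is therefore that the late rates are not interpretable as a series, not that they will flatter the device.

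**What to change.** 1. Reconcile the primary-endpoint name in section 3.2 with the definition in section 7.1.5.
2. Keep the sentence in section 8.5 that excludes imputation for other endpoints.
3. Add to sections 8.2 and 8.5, in substance: Successful aneurysm treatment is analysed in the full analysis set as time to first failure from the procedure to 5 years. The 1-, 2-, 3-, 4- and 5-year rates are read from that one curve, with 95% confidence intervals and numbers at risk. Patients who withdraw are censored at their last assessment.
4. State how deaths enter, for example as a competing event. Death is not itself a component of the composite, and 12-month all-cause mortality in the pre-approval study was 7.4% (10/136), so the rule will affect the result.
5. Label the imputed 12-month primary estimate separately, and show the 12-month value from the curve beside it.

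The cost is wording and a little more analysis. The data are already collected, and section 8.2 already applies Kaplan-Meier to secondary intervention, a component of the composite. Two limits remain. Failures found on imaging are dated only to the scan. Censoring at withdrawal also assumes that those who leave have the same later risk as those who stay, so the numbers at risk and the reasons for withdrawal need to be shown with the curve.

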8.6 Subgroup analysis

In addition to analysis of the data recorded in the full analysis and protocol sets, several subtypes were predesignated, including but not limited to subset with neck length < 15mm and neck angle greater than 60°, for example.

9、 Data Management

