7.1.4 Selection of subjects

Inclusion criteria

To be enrolled, patients must meet all the following criteria:

- Diagnosis of infrarenal abdominal aortic aneurysm
- Plan to treat with Minos™ Abdominal Aortic Stent-Graft and Delivery System
- Voluntary participation and completion of Informed Consent Form, with willingness to participate in follow-up to 5 years post-procedure.

Exclusion criteria

- Subjects in whom use of the Minos™ Abdominal Aortic Stent-Graft and Delivery System is contraindicated.

Indications:

- Abdominal Aortic Stent-Graft and Delivery System is indicated for the treatment of abdominal aortic aneurysms with a proximal neck length ≥ 15 mm.
- **Contraindications:**
 - Severe stenosis or calcification near the aneurysm, leading to difficulty in achieving apposition of vessel wall and stent graft.
 - Difficult access due to severe stenosis or tortuosity in the iliac artery or femoral artery
 - Subjects with ruptured aneurysm or acute aneurysm
 - Subjects with an infectious aneurysm.
 - Those who are allergic to contrast agents or unable to tolerate contrast agents due to renal insufficiency.
 - Patients with severe coagulation disorder and/or high risk of postoperative hemorrhage.
 - Aneurysmal neck angulation greater than 60°
 - Patients with blood supply to vital organs originating from the aneurysmal sac.
 - Patients with other comorbidities and whose life expectancy does not exceed one year
 - Subjects with connective tissue diseases, such as Marfan syndrome
 - Minors and pregnant women
 - Subjects who are allergic to nitinol
 - Subjects who are considered not suitable for treatment with stent graft.

Criteria and procedures for termination of the study/treatment

- Should severe safety concerns arise, the study shall be suspended in time.
- If the therapeutic efficacy of the investigational device is found to be poor or ineffective such that it is of no clinical value, the study shall be suspended.
- The discovery of major errors in the clinical trial protocol or significant deviation from it, making it difficult to evaluate the safety and efficacy of the investigational product.
- The sponsor requests suspension (for the reason of funds, management, etc.)
- Revocation is issued by the approving authorities.

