8.1 Population

Full Analysis Set (FAS): set of subjects that are determined according to the "Intention To Treat" principle. Refers to all subjects who signed the Informed Consent Form, met all inclusion and exclusion criteria and were treated with Minos™ system.

Per protocol set (PPS): subset of the full analysis set. Refers to all subjects in whom Minos™ system has been successfully implanted, in whom the main evaluation indicators can be observed, and in whom no significant deviations from the study protocol have been observed.

Safety set (SS): refers to all subjects who have been enrolled and evaluated for safety.

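### The predesignated subgroup with neck angle above 60° is empty by definition in both effectiveness sets, because eligibility excludes it and the FAS keeps only treated subjects who met every criterion

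*Protocol*

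**What the plan says.** Section 8.6 of the protocol names its planned subgroups by example: "including but not limited to subset with neck length < 15mm and neck angle greater than 60" degrees. It introduces them with "In addition to analysis of the data recorded in the full analysis and protocol sets" and does not name the population from which they are drawn.

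Section 7.1.4 (repeated in the Protocol Summary) has one exclusion criterion: "Subjects in whom use of the Minos™ Abdominal Aortic Stent-Graft and Delivery System is contraindicated". The list of contraindications beneath it includes "Aneurysmal neck angulation greater than 60" degrees. Neck length appears only in the indication, which says that the system "is indicated for the treatment of abdominal aortic aneurysms with a proximal neck length ≥ 15 mm". The sole anatomical inclusion criterion is "Diagnosis of infrarenal abdominal aortic aneurysm", with no neck-length threshold.

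Section 8.1 says that the FAS follows the intention-to-treat principle and then defines it: "Refers to all subjects who signed the Informed Consent Form, met all inclusion and exclusion criteria and were treated with Minos™ system". The PPS is a subset of the FAS. The Safety Set is all enrolled subjects evaluated for safety, with no eligibility condition. Section 8.2 assigns effectiveness to the FAS and PPS, and safety to the Safety Set.

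**The concern.** Two parts of the plan cannot both operate as written. Section 8.6 promises results in patients with an angle above 60°, while section 7.1.4 excludes those patients and section 8.1 removes any who are treated anyway. Section 14 foresees that subjects who meet the exclusion criterion may be enrolled and classes this as a major deviation, so the situation is not hypothetical to the authors.

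The same FAS wording has a second effect. Sections 3.1 and 7.1.1 describe the target as a real-world population. A patient who consented, received the device and was later found off-criteria is part of that population but not of the effectiveness estimate. Section 4 says that necks angled above 60° or landing zones under 15 mm raise the probability of endoleak and stent displacement. Persistent type I or III endoleak, and secondary intervention for endoleak or migration, count against success in section 7.1.5. The direction of any resulting error is therefore towards a higher reported success rate. At stake are a planned analysis that returns nothing and a headline rate whose label does not match its population.

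**Working it through.** **Membership of the subgroups.** This is set logic on the definitions.

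1. FAS = consented, met all criteria, and treated (8.1).
2. Angle above 60° is a contraindication, so the exclusion criterion applies (7.1.4). Such a subject has not met all criteria and is not in the FAS.
3. The PPS lies within the FAS, so the subject is not in the PPS either.
4. Hence, in both effectiveness sets:
   - angle above 60°: 0 subjects by definition;
   - neck below 15 mm and angle above 60° jointly: 0 by definition;
   - neck below 15 mm alone: not necessarily 0. A short neck is outside the indication, but it is not a listed contraindication and no inclusion criterion sets a neck length.
5. In the Safety Set no neck subset is empty by definition.

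**Possible effect on the success rate.** The protocol gives no planned success rate for this study. Section 4 reports 121/136 = 88.97%, that is 89%, as the 12-month clinical success rate of the earlier investigation. It is used here only for scale.

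Let p be success in subjects who met all criteria, v the share of treated subjects who did not, and q success in that share. The FAS reports p, and all treated subjects give (1 − v)p + vq. The difference is v(p − q). The documents give neither v nor q, so both are assumptions.

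With p = 89% and q = 75%:

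- v = 10%: 0.9 × 89 + 0.1 × 75 = 87.6%, a gap of 1.4 points;
- v = 20%: 0.8 × 89 + 0.2 × 75 = 86.2%, a gap of 2.8 points.

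A wider range, with p = 121/136 and q from 80% to 60%:

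| v (assumed) | Gap at q = 80% | Gap at q = 60% |
|---|---|---|
| 0% | 0 | 0 |
| 5% | 0.45 points | 1.45 points |
| 10% | 0.90 points | 2.90 points |
| 20% | 1.79 points | 5.79 points |

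The gap is also zero at any v if q = p. For comparison, the exact 95% interval for 178/200 = 89% runs from 83.8% to 93.0%, a half-width of (93.0 − 83.8)/2 = 4.6 points. The 1.4 to 2.8 point gap is smaller than that half-width. It would, however, be a systematic shift that a larger sample does not reduce.

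**The case against.** The best defence has four parts.

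- **Source population.** Section 8.6 presents the subgroups as additional to the FAS and PPS analyses. If they are drawn from the Safety Set, they need not be empty. This stands as a reading, but section 8.2 assigns no effectiveness analysis to the Safety Set, so an effectiveness result for the angle subgroup still has no home.
- **Outcomes are not lost.** Section 3.2 classes migration, stenosis, occlusion and mortality as safety indicators. Section 13.1 lists type I/III endoleak and migration as device-related adverse events, which section 8.2 tabulates. Section 14 has major deviations reported. This stands: what goes missing is the contribution to the effectiveness estimate, not the record of the event.
- **Legitimate target.** The FAS estimate is valid for patients who met the criteria. That stands too, but it is not what the intention-to-treat label or the real-world objective describes.
- **Descriptive study.** Section 8.3 states that there is no formal hypothesis test, so no confirmatory decision rests on the subgroup. This lowers the severity.

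Three stronger readings are tempting, and the documents do not support them. A reader might infer that short necks are also excluded by eligibility, so that every planned neck subgroup is empty. The protocol does not say that, and the wording of 8.6 may mean two separate subsets. A reader might infer that effectiveness is in fact inflated. That requires off-criteria patients to be treated and to do worse: section 4 supports only the direction, and no count or rate is given. A reader might also infer from the late determination of the analysis population in section 9.3 that failed cases would be reclassified as ineligible. Nothing in the text says that eligibility is re-judged in the light of outcome.

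**Conclusion.** The point holds in limited form. The contradiction for angle above 60°, alone or jointly with a short neck, is certain from the text: both effectiveness sets contain no such subject by definition. Whether a short-neck subset can be populated is unresolved, because the protocol does not state the eligibility of neck length below 15 mm.

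The statement about the success rate is conditional. It may be overstated, by an amount the documents do not fix: zero with no off-criteria implants, 1.4 to 2.8 points under the assumptions of 10% to 20% off-criteria and 75% against 89% success, and up to about 6 points at the edge of the wider assumed range. The contradiction does not depend on these figures. Since the study is descriptive and the Safety Set keeps the safety outcomes, this should be fixed but does not invalidate the design.

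**What to change.** - Define the main effectiveness set as all consented subjects in whom implantation of the Minos system was attempted, regardless of eligibility violations found later. Show the met-all-criteria population as a sensitivity analysis. If the present FAS is kept as the main set, drop the intention-to-treat label.
- In section 8.6, run the neck-anatomy subgroups in the all-attempted set, state whether neck length and angle are separate or joint subsets, and describe cases above 60° as off-criteria implants while the exclusion stands.
- Reconcile sections 7.1.4, 8.1 and 8.6 on whether these anatomies are eligible, including an explicit statement on neck length below 15 mm. Which anatomy should be treated is for the sponsor and investigators and is not judged here.

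The cost is wording in the protocol and the matching analysis plan, with no added subjects or visits, and possibly a slightly lower headline success rate.
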